Despite the high success rate of anti-reflux surgery, reoperation does occur. The indication for reoperation is most often recurrence of reflux symptoms or dysphagia, and reoperation should be preceded by thorough investigation and possible endoscopic balloon-dilation (15). Laparoscopic reoperation is both feasible and safe, but has been linked to higher morbidity, higher risk of conversion to open surgery and longer length of stay. The final result seem to result in less patient satisfaction than primary surgery, but the available evidence is limited by a high risk of bias due to small sample size and a possible underreporting of complications (16, 17).

An American study reported a cumulative five- and ten year incidence of reoperation of 5.2% and 6.9% respectively. The rate of reoperation was highest in the first year after primary anti-reflux surgery. 30% of reoperations were performed in a different center than the primary procedure. In a Danish study, Funch-Jensen et al (18), investigated rate of reoperation in Denmark 1997-2005 and calculated a rate of 5% without significant differences in length of stay, rate of complications or mortality compared to primary

surgery. Reoperation was however associated with a higher rate of conversion to open surgery with a tendency towards higher rates of conversion in low-volume centers. As in the American study, reoperation was often performed at different centers than the primary procedure. Whether this was the result of centralization or patient's wishes is unknown.

It is our hypothesis, that from 2000-2017, reoperative anti-reflux surgery was performed primarily with a laparoscopic approach without increased length of stay or rate of complications compared to primary surgery. Due to increased surgical experience the rate of complications is decreasing despite increased comorbidity. Endoscopic balloon-dilatation delays reoperation but does not prevent it.

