## Methods

The study is a two-part register-based cohort study based on data from The National Patient Registry, The Civic Registry and Danish Anaesthesia Database in the period 1996-2017. The two individual parts of the study concerns the same population.

The population is defined as all adult Danish patients undergoing anti-reflux surgery (Nomesco: KJBC00, KJBC01, KJBC02, KJBW96, KJBW97) from 2000-2017 identified from The National Patient Register.

Age, sex, Charlson Comorbidity Index at date of surgery and length of stay in relation to any surgery and any surgical or endoscopic procedure performed after anti-reflux surgery (including diagnosis 30 days postoperatively to establish possible morbidity) are derived from the National Patient Registry.

ASA-score, weight, height, use of alcohol or tobacco and priority of any surgery (emergency or planned) during the study period are retrieved from The Danish Anaesthesia Database. From the Civic Register, data on mortality in the study period are retrieved.

Information on the use of pharmacological treatment for gastroesophageal reflux disease on population level is retrieved from MEDSTAT and data on population size on population level are retrieved from Statistics Denmark.

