## Statistical analysis

### 1) Course of illness leading to reoperative anti-reflux surgery

Data will be analyzed using STATA15. Descriptive analysis of age, sex, comorbidity (Charlson Comorbidity Index, ASA-score, BMI, alcohol/tobacco use), complications to surgery, rate of endoscopic dilation and mortality comparing patients with only primary anti-reflux surgery and patients with reoperation during the study period, will be performed using Student's t-test, Chi2-test and Mann-Whitney-U test.

Logistic regression will be performed with reoperation (laparoscopic, open or other) as primary outcome and age, sex, comorbidity (Charlson Comorbidity Index, ASA-score, BMI, alcohol/tobacco use), complications to surgery and endoscopic or surgical procedure during study period as independent variables. If the number of patients is sufficient, subanalysis will be performed with emergency reoperation as dependent variable/outcome.

Secondary analysis will be performed using Cox-regression investigating time to reoperation with age, sex, comorbidity (Charlson Comorbidity Index, ASA-score, BMI, alcohol/tobacco use), complications to surgery and endoscopic or surgical procedure during study period as independent variables.

*2) Utilization of treatment of gastroesophageal reflux disease.*

The rate of anti-reflux surgery per 100.000 inhabitants for each year during the study period will be calculated using census data from Statistics Denmark. From MEDSAT the rate of use of pharmacological anti-reflux treatment per 100.000 inhabitants will be calculated using abovementioned census-data. Trends in the utilization of surgery are investigated with trend-analysis in the form of Poisson-regression alternatively negative binominal regression.

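### Both regressions adjust the baseline risk factors for postoperative complications and procedures, and no adjusted model without those terms is planned, so the baseline coefficients cannot be read as overall associations with reoperation.

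*Combined protocol and SAP*

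**What the plan says.** Statistical analysis, part 1, sets out two regressions. The primary one reads "Logistic regression will be performed with reoperation (laparoscopic, open or other) as primary outcome". The other reads "Secondary analysis will be performed using Cox-regression investigating time to reoperation". Both have the same covariates: "age, sex, comorbidity (Charlson Comorbidity Index, ASA-score, BMI, alcohol/tobacco use", followed by "complications to surgery and endoscopic or surgical procedure during study period as independent variables".

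The Methods section gives the timing. It takes "Charlson Comorbidity Index at date of surgery" from the National Patient Registry, along with "any surgical or endoscopic procedure performed after anti-reflux surgery (including diagnosis 30 days postoperatively to establish possible morbidity". So the Charlson index belongs to the day of the operation, while the procedures and the diagnoses used to establish morbidity come after it. ASA score, weight, height, alcohol and tobacco come from the anaesthesia database. They have no stated index date.

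Before the regressions, the same section plans t, Chi2 and Mann-Whitney comparisons between patients with and without a reoperation. These cover the baseline factors one at a time, without adjustment.

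The Background bears on the pathway in two places: "reoperation should be preceded by thorough investigation and possible endoscopic balloon-dilation" and "Due to increased surgical experience the rate of complications is decreasing despite increased comorbidity". It also hypothesises that dilatation postpones a reoperation without averting it.

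**The concern.** A model that holds a later event fixed estimates what remains of a baseline factor's association once that event is accounted for. If smoking or comorbidity leads to reoperation partly through a complication, or through dysphagia that is dilated, that part passes to the complication or dilatation term. The smoking or comorbidity coefficient then shows only the rest.

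There is a second difficulty. Symptom severity is not among the variables retrieved, and it plausibly drives both dilatation and reoperation. Conditioning on dilatation then links the baseline factor to severity, and the coefficient can move away even from the direct effect.

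At stake is how the main results table is read. Every adjusted baseline estimate would come from such a model. A reader who takes the estimates as overall associations would tend to understate factors that work through the postoperative course.

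This is separate from how procedures are timed in the model. A procedure term coded correctly as time-dependent would still take up the mediated part.

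**Working it through.** The plan gives no sample size, event count or effect size for these models, so there is no figure of its own to reproduce. The check has a textual part and an illustration.

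**Text: is each link in the documents?**

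| Link | Support in the documents |
|---|---|
| Terms come after baseline | Yes: Methods, for procedures and 30-day diagnoses |
| Dilatation to reoperation | Yes: Background puts possible dilatation before reoperation and hypothesises an effect on its timing |
| Comorbidity to complications | Implied only, by the word despite in a sentence on time trends |
| Complications to reoperation | Not stated; the usual indications named are recurrent reflux and dysphagia |
| BMI, alcohol or tobacco to either | Not stated |
| Adjusted model without the later terms | None |

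The order in time is established. A complete chain is plausible, but the documents state none for any one factor.

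**Illustration by hand.** All inputs are assumed, chosen to lie near the 5% Danish reoperation rate in the Background. Let d be the probability of dilatation (0.08 without the factor, 0.16 with it), and let the reoperation risk be r0 = 0.035 without and r1 = 0.20 with dilatation.

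Risk = (1 − d) × r0 + d × r1

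- Without the factor: 0.92 × 0.035 + 0.08 × 0.20 = 0.0322 + 0.0160 = 4.82%
- With the factor: 0.84 × 0.035 + 0.16 × 0.20 = 0.0294 + 0.0320 = 6.14%
- Total OR = (0.0614/0.9386) / (0.0482/0.9518) = 0.0654/0.0506 = 1.29
- OR given dilatation status = 1.00, by construction, because r0 and r1 do not depend on the factor

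Now add a direct OR of 1.2 in those with the factor:

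- r0: odds 0.0363 × 1.2 = 0.0435, risk 4.17%
- r1: odds 0.25 × 1.2 = 0.30, risk 23.08%
- Risk with the factor: 0.84 × 0.0417 + 0.16 × 0.2308 = 7.20%
- Total OR = (0.0720/0.9280) / 0.0506 = 1.53, against 1.20 after adjustment
- Share of the log-OR removed: 1 − ln 1.20 / ln 1.53 = 1 − 0.182/0.426 = 57%

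The result depends heavily on the inputs. With the same r0 and r1, dilatation of 5% versus 16% gives a total OR of 1.45; equal dilatation in both groups gives 1.00.

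**Illustration by simulation.** 2,000,000 patients per setting. Assumed: factor prevalence 30%, later event in 10% of those without the factor, direct OR 1.3. The overall reoperation risk was set at 5%.

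| OR factor to event | OR event to reoperation | Total OR | OR adjusted for the event | Log-OR removed |
|---|---|---|---|---|
| 1.5 | 2 | 1.36 | 1.31 | 12% |
| 2 | 5 | 1.57 | 1.30 | 42% |
| 3 | 10 | 2.11 | 1.29 | 66% |
| 1 | 5 | 1.29 | 1.30 | none |
| 2 | 1 | 1.29 | 1.29 | none |

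Next, an unmeasured cause shared by event and reoperation was added (prevalence 30%). With links of 2 and 5:

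- Unmeasured cause OR 3 on each: adjusted OR 1.25, true direct OR 1.3.
- Unmeasured cause OR 5 on each: adjusted OR 0.92, true direct OR 1.0.

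With links of 3 and 1 (event without effect on reoperation) and the unmeasured cause at OR 5 on each, the adjusted OR was 1.15, true direct OR 1.3. So this distortion needs only that the factor affects the event and that a common cause is missing from the model.

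**The case against.** The strongest reply is that the plan never says it wants total effects. Its aim is to follow the illness up to reoperation, and for that question a joint model of patient factors and postoperative events is a legitimate choice. It is not wrong in itself if prediction during follow-up or direct effects are meant. This stands, and it limits the point to how the baseline coefficients may be read. It does not remove the point: no target is stated, direct effects would need an assumption of no unmeasured cause shared by the later events and reoperation, and no adjusted estimate of the other kind is planned.

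Three stronger readings are tempting and are not supported:

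- *That the Background shows complications to be a step towards reoperation.* It ties dilatation to reoperation. For complications it offers only an implied link from comorbidity, and nothing onward.
- *That risk factors will be reported as having no effect.* That follows only for a factor acting wholly through the adjusted events; a partly mediated factor is attenuated. The unadjusted comparisons would also still show a crude association, although they do not replace an adjusted model.
- *That the estimates are meant for advising patients before primary surgery.* The documents state no such use.

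It can also be objected that a baseline-only model presumes baseline timing. Only the Charlson index is dated to the operation. That is correct, and the fix has to state the timing for the other variables.

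**Conclusion.** The point holds as one of interpretation and of a missing model. As planned, each baseline coefficient in both regressions is a residual association given postoperative events, and it must not be read as the factor's overall effect. This includes age and sex. The coefficient is attenuated to the extent that the factor acts through complications or dilatation in the same direction as its direct part, and it may be further distorted by unmeasured severity.

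The size cannot be derived from the documents. Under the assumed values it runs from no loss, when either link is absent, through 12% to 66% of the log odds ratio in the simulated settings with a 1.3 direct OR, to the whole association when there is no direct effect (1.29 to 1.00). These figures show what could happen and are not estimates for this cohort. The structural part rests on the plan's own text and is firm; the consequence rests on a plausible but assumed chain.

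**What to change.** In Statistical analysis, part 1, specify two models for the logistic analysis and two for the Cox analysis.

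- **Model 1:** age, sex, Charlson index, ASA score, BMI and alcohol/tobacco use only, all taken from the index operation record. Report the baseline risk-factor associations from this model.
- **Model 2:** Model 1 plus complications and the procedures that precede reoperation, with procedures entered as time-dependent terms in the Cox analysis. Use it to report those postoperative terms, not the baseline factors.

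Add one sentence saying that the baseline coefficients of Model 2 are conditional on the postoperative course and are not overall effects.

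The cost is one extra model and one table column per analysis, with no new data. Comparing the two columns will also show how far the baseline coefficients move once the later events are added.

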## Aim

The purpose of this study is to investigate course of illness leading to reoperation after primary anti-reflux surgery and investigate the utilization of anti-reflux treatment, both medical and surgical, in the period 2000-2017

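### Procedures occurring after the index operation enter a logistic model that ignores follow-up of 0 to about 18 years, so their odds ratio is biased under either workable coding; the Cox model lacks a timing rule and a dilation term

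*Combined protocol and SAP*

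**What the plan says.** The Aim section of the combined protocol and SAP opens with the intention to "investigate course of illness leading to reoperation after primary anti-reflux surgery". The Background ends with the hypothesis "Endoscopic balloon-dilatation delays reoperation but does not prevent it".

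The statistical analysis, section 1, names reoperation as the primary outcome of a logistic regression and gives a Cox regression for time to reoperation as secondary. Both covariate lists end with "endoscopic or surgical procedure during study period as independent variables". Dilation is named on its own only in the descriptive comparison of patients with and without reoperation.

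The Methods define the population as adults "undergoing anti-reflux surgery (Nomesco: KJBC00, KJBC01, KJBC02, KJBW96, KJBW97) from 2000-2017" and collect "any surgical or endoscopic procedure performed after anti-reflux surgery". That sets a lower time limit. The upper limit is the end of the study period. No section places a limit at reoperation, excludes the reoperation from the procedures counted, allows for unequal follow-up in the logistic model, or states whether the Cox covariate is fixed or time-dependent.

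**The concern.** A dilation or endoscopy after the index operation is not a baseline characteristic. Whether a patient has one depends on how long the patient is observed, and so does whether the patient is reoperated. A logistic model without a time axis turns that shared dependence into an association. If exposure is instead counted only up to reoperation, reoperated patients have less time in which to become exposed, and the association is distorted the other way.

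At stake is the first aim, and in particular the dilatation hypothesis: these two models are the only planned regressions that could bear on it. Analysts could choose among codings whose null results lie on both sides of 1. A covariate that pools dilation with every other endoscopy or operation does not isolate dilation in any case.

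**Working it through.** The plan gives no expected odds ratio or hazard ratio and no dilation rate, so there is no figure of its own to reproduce. The check asks what each coding returns when dilation has no effect.

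**Inputs from the documents.** The Background states: "An American study reported a cumulative five- and ten year incidence of reoperation of 5.2% and 6.9% respectively" and "The rate of reoperation was highest in the first year after primary anti-reflux surgery". Entry is 2000-2017 and data end in 2017. The five-year figure gives a mean hazard of -ln(1 - 0.052)/5 = 0.01068 per year.

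**Hand check 1: dilations at any time, unequal follow-up.** Assume dilation at 5% per year, independent of reoperation, no deaths, and half the patients followed for 5 years and half for 10.
- Dilated: 1 - exp(-0.25) = 0.2212 and 1 - exp(-0.50) = 0.3935. Reoperated: 0.052 and 0.069. Within each half the odds ratio is 1 by construction.
- Pooled, both events: (0.052 × 0.2212 + 0.069 × 0.3935)/2 = 0.01933.
- Reoperated only: 0.0605 - 0.01933 = 0.04117. Dilated only: 0.30733 - 0.01933 = 0.28800. Neither: 0.65150.
- Odds ratio = (0.01933 × 0.65150)/(0.04117 × 0.28800) = 1.06.

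**Hand check 2: only dilations before reoperation, everyone followed for 5 years.** With h = 0.01068 and d = 0.05:
- Reoperated without earlier dilation: h/(h + d) × (1 - exp(-5(h + d))) = 0.04606. Reoperated after dilation: 0.05200 - 0.04606 = 0.00594.
- Not reoperated: dilated 0.948 × 0.2212 = 0.20970; undilated 0.948 × 0.7788 = 0.73830.
- Odds ratio = (0.00594 × 0.73830)/(0.04606 × 0.20970) = 0.45, although follow-up is equal.

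**Simulation over the planned entry period.** Entry is uniform over 2000-2017, with reoperation at 5.2% by 5 years and 6.9% by 10. Assumed: 1.5, 2 or 3% reoperated by 1 year; 8.5% by 18 years; death 1% per year; first dilation at 2 or 5% per year during the first 2, 5 or 18 years. That is 3 × 2 × 3 = 18 scenarios, with dilation as the only covariate.

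| Coding, no true effect | Estimate |
|---|---|
| Logistic, any time | OR 1.05-1.37 |
| Logistic, any time, stratified by length of follow-up | OR 0.99-1.02 |
| Logistic, before reoperation or censoring | OR 0.30-0.85 |
| Cox, fixed, any time | HR 0.99-1.03 |
| Cox, fixed, before reoperation | HR 0.23-0.80 |
| Cox, time-dependent | HR 0.98-1.03 |

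The second row identifies the cause of the upward bias as unequal follow-up, since it returns to 1 with no cut-off. The third row shows that a cut-off alone moves the odds ratio further from 1.

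**With a true hazard ratio of 0.70:** any-time odds ratio 0.82-1.20, any-time Cox 0.77-0.92, time-dependent Cox 0.69-0.72. Any-time Cox coding is near 1 under the null but dilutes a real effect.

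**Delay or prevention.** One time-dependent hazard ratio is 0.66-0.72 if dilation postpones reoperation by 3 years and prevents none, and 0.68-0.71 if it prevents reoperation in 30% of dilated patients. Split at 3 years after dilation, pure delay gives 0 and then 1.48-1.70; prevention gives 0.68-0.73 and then 0.64-0.71. Only the split separates them.

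**The case against.** Several objections have force.

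- *The missing cut-off is not the cause.* Correct for the base case. The absence of a cut-off matters in itself only if procedure rates change after reoperation or the reoperation is counted. With equal 10-year follow-up and no cut-off the null odds ratio is 0.99-1.00; it becomes 2.38-2.56 if the dilation rate is assumed to triple after reoperation. The documents give no such rate. Stratifying by follow-up or using a fixed horizon is thus a possible remedy, but it depends on that unchanged rate and still lets procedures after the outcome count as predictors.
- *The reoperation would not be counted as its own predictor.* A reader might infer that every reoperated patient is exposed and the model cannot be estimated. The documents do not support that: reoperation is named as the outcome and procedures are listed separately, so the ordinary reading excludes it. The wording should say so, and no more follows.
- *The aim implies prior procedures.* The phrase about illness leading to reoperation does point that way. It selects the coding with a null odds ratio of 0.30-0.85, so it does not rescue the logistic model.
- *The Cox model is not shown to be wrong.* Accepted. Time-dependent coding is not ruled out, and separate terms are possible; the plan states neither.
- *The plan does not tie either regression to the dilatation hypothesis.* True, but no other planned regression could address it.
- *The bias may be small.* With dilations confined to the first 2 years the any-time bias is at the low end of its range. The checks are also unadjusted, whereas the planned models are not.

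**Conclusion.** The concern holds in this form. For a post-index procedure, the logistic model as specified gives a biased odds ratio under both workable codings: about 1.05-1.37 or about 0.30-0.85 when the truth is 1. For the Cox model the fault is a gap in specification. A fixed pre-reoperation covariate would carry immortal-time bias (null hazard ratio about 0.2-0.8), and neither regression states a dilation term.

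The sizes rest on assumed dilation rates of 2-5% per year, independent of reoperation; the directions follow from the coding. They do not predict the study's result. The Background says "reoperation should be preceded by thorough investigation and possible endoscopic balloon-dilation", so confounding by indication would push estimates upward, on top of these biases. The hypotheses on surgical approach, length of stay and complications are not affected.

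**What to change.** 1. Remove procedures after the index operation from the logistic model.
2. In the Cox model, enter endoscopic dilation as its own time-dependent covariate: 0 until the first dilation after the index operation, 1 from then on. End follow-up at reoperation, death or the end of 2017. Code other post-index procedures in the same way, and exclude the reoperation codes from them.
3. Name this Cox model as the analysis of the dilatation hypothesis, and let the dilation effect differ before and after a time since dilation that is fixed before the data are seen.
4. Report the result as an association, because confounding by indication remains.

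Optional additions are a landmark comparison of cumulative incidence with death as a competing event, a before-reoperation cut-off and person-year bands for the descriptive dilation rate, and an explicit link between complications and the index operation.

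The cost is a few sentences in the SAP and splitting of records at procedure dates, which the planned time-to-reoperation analysis already presupposes. The logistic model would no longer speak to dilation. Precision will be limited: the null simulation gives 1.5-8.6 reoperations after dilation per 1,000 index patients, or about 5 to 26 among an assumed 3,000 (3 × 1.5 to 3 × 8.6). The 95% interval would then run from the hazard ratio divided by 1.6-2.6 to the hazard ratio multiplied by the same factor, and would be wider within each period since dilation. An interval that includes 1 must not be read as showing that dilation does not prevent reoperation.

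### The endoscopic predictor of reoperation is wider than the dilatation hypothesis and, as worded, can count work-up for the redo as a predictor of the redo

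*Combined protocol and SAP*

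**What the plan says.** Methods states that the National Patient Registry extraction covers "any surgical or endoscopic procedure performed after anti-reflux surgery". Statistical analysis, part 1, then lists "endoscopic or surgical procedure during study period as independent variables" in the logistic model, which carries the primary outcome, and again in the Cox model ("Secondary analysis will be performed using Cox-regression investigating time to reoperation").

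Elsewhere the endoscopic interest is narrower. The hypothesis at the end of the Background reads "Endoscopic balloon-dilatation delays reoperation but does not prevent it". The descriptive comparison in Statistical analysis, part 1, covers "rate of endoscopic dilation and mortality comparing patients with only primary anti-reflux surgery and patients with reoperation during the study period".

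The Background also says that "reoperation should be preceded by thorough investigation and possible endoscopic balloon-dilation".

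The plan gives no endoscopy codes and does not separate diagnostic from therapeutic endoscopy. It has no rule for procedures belonging to the redo work-up, no lag and no time-dependent coding.

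**The concern.** An endoscopy done because a redo is being considered is a step in the decision to reoperate. Entered as an independent variable, it makes the outcome partly generate its own predictor.

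This is separate from counting procedures that follow the redo, and from coding exposure as ever/never from day 0. Both of those are cured by dating. A work-up endoscopy truly precedes the redo, so it stays in the exposed category after procedures are dated, cut off at the redo and coded as time-dependent. Someone who repaired only the dating would still have a biased term.

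The study aims to describe the course of illness leading to reoperation, so a raised coefficient for endoscopy would readily be reported as a risk factor. A dilatation done on the way to a planned redo raises the same difficulty for the dilatation hypothesis.

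**Working it through.** The plan has no sample size, power or effect figure for this term, so there is nothing to reproduce. The check asks what the models return when endoscopy has no effect on reoperation.

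**Inputs from the documents (Background).** The cited American study gives a "cumulative five- and ten year incidence of reoperation of 5.2% and 6.9% respectively" and adds: "The rate of reoperation was highest in the first year after primary anti-reflux surgery".

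**Assumptions, not in the documents.** Reoperation is 2% at 1 year. Background endoscopy is 3–10% per year and unrelated to redo. The share w of redos with a work-up endoscopy is 0, 10, 30 or 60%. Work-up falls 0.02–0.5 years before the redo. Follow-up is uniform over 0–18 years.

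**Redo hazard per year.**
- Year 1: −ln(0.98) = 0.0202
- Years 1–5: [−ln(0.948) + ln(0.98)]/4 = (0.0534 − 0.0202)/4 = 0.0083
- Years 5–10: [−ln(0.931) + ln(0.948)]/5 = (0.0715 − 0.0534)/5 = 0.0036

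**Hand check of the mechanism.** Suppose a proportion p of patients at risk have already had a background endoscopy. Under no effect, a redo patient is exposed with probability p + w(1 − p), and any other patient with probability p. The ratio of exposure odds, which approximates the time-dependent hazard ratio, is

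[p + w(1 − p)] / [(1 − w)p] = 1 + w / [p(1 − w)].

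This exceeds 1 for every w above 0. With p = 0.10 as an illustration:
- w = 0.10: 1 + 0.10/0.09 = 2.1
- w = 0.30: 1 + 0.30/0.07 = 5.3
- w = 0.60: 1 + 0.60/0.04 = 16

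**Simulation.** 400,000 patients per scenario, true effect nil, procedures correctly dated and cut off at the redo. Ranges run over background rates of 3–10% per year.

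| Share of redos with work-up endoscopy (assumed) | Cox, time-dependent: HR | Logistic, ever/never: OR |
|---|---|---|
| 0% | 1.0 | 0.3–0.4 |
| 10% | 1.6–2.3 | 0.5–0.8 |
| 30% | 3.7–7.3 | 0.85–2.0 |
| 60% | 14–31 | 2.2–6.2 |

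A repeat run agreed to within simulation error. A separate simulation with fixed 10-year follow-up and background rates of 2–20% per year gave hazard ratios of 0.97–1.01 with no work-up endoscopy, 1.4–3.1 at 10%, 2.4–7.5 at 25% and 5.9–27 at 50%.

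**Why the logistic column starts below 1.** Exposure is counted only up to the redo, so redo patients have less time in which to have a background endoscopy. That alone gives 0.3–0.4. Work-up pushes the odds ratio up from there.

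**Effect of a lag in the Cox model.** When all work-up falls within 6 months, a 6-month lag returns the hazard ratio to 0.98–1.03. When work-up can fall up to 12 months before the redo (separate simulation, background 5–10% per year), a 180-day lag leaves 2.4–3.3 at a 50% share and 4.7–7.2 at 90%. A 365-day lag gives 0.97–1.02. The lag works only if it covers the work-up interval, and the documents do not give that interval.

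**The case against.** The strongest reply is that the authors meant dilatation. The plan never mentions diagnostic endoscopy, the unrestricted wording in Methods describes data retrieval rather than a covariate, and the only endoscopic procedure named is dilatation. This stands in part: inclusion of diagnostic endoscopy follows from the wording and is not stated outright. But the same section uses the narrow term in the descriptive comparison and the wide term in both regressions, so an analyst following the text would include it. If dilatation was meant, one line settles the matter.

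The second reply concerns size. A reader might infer that the plan would report hazard ratios of 14–31, or that endoscopy must be among the strongest predictors. The documents do not support that. They give no share of redos with endoscopic work-up, no timing and no background rate. The hazard ratios belong to a time-dependent Cox model that the plan does not specify. In the primary logistic model the odds ratio can lie on either side of 1.

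Third, a 6-month lag as the main analysis might look like a cure. Its success is built in when the simulated work-up falls within 6 months. It also excludes exposed time in the first 6 months, although the redo rate is highest in the first year and the hypothesis is about delay.

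Finally, part of the aim is descriptive. Endoscopy before a redo is a legitimate finding about the pathway; it misleads only when read as a factor leading to reoperation.

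**Conclusion.** The point holds in a limited form and should be dealt with before the models are run. The endoscopic term is wider than the hypothesis and, taken literally, admits work-up endoscopy, which the Background implies but does not quantify. The resulting bias is upward and survives correct dating.

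In a time-dependent Cox model it is modest to substantial at a 10% work-up share and large from 30%. In the primary logistic model the work-up component is also upward, but it is mixed with the opposite bias from unequal time at risk, so neither the net direction nor a large positive association is certain. All sizes rest on the assumed work-up share, work-up timing and background endoscopy rate.

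**What to change.** **Both models.** Define the endoscopic term as therapeutic balloon-dilatation and list the procedure codes. Remove diagnostic endoscopy from the predictors and report its frequency and timing before redo as part of the pathway.

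**Cox model.** Enter dilatation as a time-dependent exposure. Add lagged sensitivity analyses, for example 3, 6 and 12 months, with the longest covering the work-up interval seen in the data.

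**Logistic model.** Do not count dilatations within the same window before the redo, or present the term as descriptive only. The window removes the work-up component but not the bias from unequal time at risk, so even then the odds ratio should not be read as an effect of dilatation.

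**Cost.** Plan wording and a little coding; the procedures are already being extracted. There will be fewer exposed events, and early effects of dilatation are left out of the lagged estimates. Confounding by indication remains, because patients who are dilated differ from those who are not, and should be stated as a limitation.
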